### **4.3 WITHDRAWAL OF SUBJECTS FROM THE STUDY**

#### **4.3.1 Reasons for Withdrawal**

Subjects can withdraw consent and discontinue from the study or from treatment at any time, for any reason, without prejudice to further treatment.

The investigator may withdraw a subject from the study or from treatment if the subject:

1. Is noncompliant with the protocol requirements;
2. Experiences an SAE or intolerable AE(s) that in the investigator's opinion requires withdrawal from the study;
3. Becomes pregnant;
4. Is required to take a medication prohibited by the protocol; or
5. Requests an early discontinuation for any reason.

The investigator can also withdraw a subject upon the request of the sponsor, or if the sponsor terminates the study. Upon occurrence of an SAE or intolerable AE, the investigator will confer with the sponsor. If a subject is discontinued because of an AE, the event will be followed until it is resolved, stable, or judged by the investigator to be not clinically significant.

#### **4.3.2 Handling of Withdrawals**

Subjects are free to withdraw from the study at any time upon request. Subject participation in the study may be stopped at any time at the discretion of the investigator or at the request of the sponsor.

When a subject withdraws from the study, the reason(s) for withdrawal shall be recorded by the investigator on the relevant page of the eCRF. Whenever possible, any subject who withdraws from the study prematurely will undergo all EOS assessments. Any subject who fails to return for final assessments will be contacted by the site in an attempt to have them comply with the protocol. The status of subjects who fail to complete final assessments will be documented in the eCRF.

All subjects who prematurely discontinue study treatment should be encouraged to remain in the study and maintain the same protocol schedule and assessments as described in [Table 3-1](#). This will allow for continued subject follow-up for key outcome data.

### **4.3.3 Replacements**

In the event there is at least one subject who withdraws without post-baseline virology data, with the exception of those who withdraw for safety or tolerability, enrollment may remain open or extended at each dose level/cohort to enroll additional randomization block(s) of 4 patients (3:1) to increase the likelihood that at least 15 active and 5 placebo subjects with evaluable virology data are included in each cohort. Any additional patients will be randomized through the same centralized randomization process.

## **5. STUDY TREATMENTS**

### **5.1 TREATMENTS ADMINISTERED**

All subjects will receive the study treatments as described in [Section 3](#). The time of the initial study drug administration will be called “0” hours. The study drug will be administered with approximately 240 mL of water. Up to an additional 240 mL of water will be allowed, if necessary, to aid in swallowing of the study drugs. Subjects will not engage in strenuous activity at any time during the treatment period. When morning blood draws are required, study drug will be administered after blood sample collection. Study drug may be taken with or without food. The timing of TID dosing is provided in [Section 3.1.2](#) and the timing of BID dosing is provided in [Section 3.1.3](#). Doses of AT-752 and matching placebo should be separated by 8 hours ( $\pm 2$  hours) for TID dosing and by 12 hours ( $\pm 2$  hours) for BID dosing. After Day 1, if a dose is delayed, it should be taken as soon as possible, but must be taken at least 6 hours before the next scheduled dose. Otherwise, the dose must be skipped and the next dose taken as scheduled. Study drug dose modifications are not permitted in the study.

Dosing will be stopped at the end of the 15-dose (TID) or 10-dose (BID) treatment period. At the end of treatment period, tablets corresponding to any missed doses should be returned to the site.

Subjects must take the dose that was assigned at randomization, unless they discontinue for one of the reasons noted in [Section 4.3.1](#).

### 5.1.1 Safety Review Committee

This study is designed such that moving to the next dosing cohort is allowed only after an unblinded safety data review of the previous cohort by the SRC.

Unblinded safety summaries (e.g., AEs, clinical laboratory test results, vital sign measurements, and 12-lead ECG results) will be reviewed by the SRC to evaluate safety and tolerability of a given dose.

Initiation of additional cohorts will occur based on an initial safety review by the SRC of available safety data (through Day 5) and available PK data of the prior cohort.

CCI [REDACTED]

[REDACTED]

[REDACTED]

[REDACTED]

[REDACTED]

[REDACTED]

[REDACTED]

[REDACTED]

[REDACTED]

[REDACTED]

[REDACTED]

[REDACTED]

[REDACTED]

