The dose level for Cohort 1 (750 mg TID) was determined based on review of PK and safety data from the Phase 1 healthy volunteer study (Protocol AT-02A-001). In healthy subjects, this dose was able to rapidly achieve and maintain AT-273 troughs plasma concentrations above 200 ng/mL (in vitro EC90 of AT-281 against DENV-2 is 0.64 µM or approximately 200 ng/mL equivalent of AT-273) and was well-tolerated. Specific doses for Cohort 2 and Cohort 3 will be endorsed by the Safety Review Committee (SRC) after an unblinded review of the previous cohort by the SRC.

- Cohort 1: 750 mg AT-752/placebo TID for 5 days
- Cohort 2: up to 1000 mg AT-752/placebo BID or TID for 5 days
- Cohort 3: up to 1500 mg AT-752/placebo BID for 5 days

In each blinded cohort, subjects will be randomized to receive AT-752 or placebo in a 3:1 ratio. Each cohort will include 20 subjects (15 subjects receive AT-752 and 5 receive placebo).

Prior to the initiation of each cohort after Cohort 1, all safety and available PK data through at least 5 days in the current dose cohort will undergo an unblinded review by the SRC. Following each SRC review, the dose for the next cohort will be endorsed by the SRC and the cohort enrolled.

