**Figure 3-1 AT-02A-002 Study design**

At screening, information including demographics, medical history (including time since illness onset), and concomitant medications will be gathered from potential subjects. Additional assessments and collection of data will be conducted as indicated in the schedule of events (SOE; [Table 3-1](#)). Any clinical care necessary throughout the study, such as supportive care, will be at the discretion of the investigator and institutional guidelines. After subjects are confirmed eligible at screening, randomization and the initial dosing should

occur within 24 hours, and if possible, the initial dose should be given on the same day as screening.

Upon randomization, subjects will receive their first dose of study drug. Subjects in Cohort 1 will receive doses that are separated by approximately 8 hours ( $\pm 2$  hours; morning, mid-day, and evening). [Subjects receiving BID dosing will receive doses that are separated by 12 hours ( $\pm 2$  hours; morning and evening)]. Subjects can continue participation even if hospitalized or using mobile nursing during the study, depending on site availability and subject decision. Subjects will be discharged on Day 6 (after end of treatment) if hospitalized, and asked to return on Day 7, Day 8, and Day 14 ( $\pm 1$  day) with a final safety follow-up performed on Day 28 ( $\pm 3$  days). For clinical sites that decide to use mobile nursing, some of the subsequent visits (Days 2-5, Days 7-8, and Day 14) may be performed at investigator discretion through mobile nursing. The Day 1, Day 6, and Day 28 visits must be conducted at the clinical site. The Day 6 end of treatment visit will occur 8 to 24 hours after the last dose of study medication is administered.

Note that if the initial dose of study drug is administered on the same day as screening (at mid-day or in the evening), the last dose of study drug will be administered on Day 6. See [Section 3.1.2](#) and [Section 3.1.3](#) for detailed descriptions of TID and BID dosing, respectively.

The 3 planned sequential dosing cohorts are:

- Cohort 1: 750 mg AT-752/placebo TID for 5 days
- Cohort 2: up to 1000 mg AT-752/placebo BID or TID for 5 days
- Cohort 3: up to 1500 mg AT-752/placebo BID for 5 days

In each blinded cohort, subjects will be randomized to receive active drug or placebo in a 3:1 randomization. Each cohort will include 20 subjects (15 subjects receive AT-752 and 5 subjects receive placebo).

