Specific doses for Cohort 2 and Cohort 3 will be endorsed by the SRC) after an unblinded review of the previous cohort by the SRC. Prior to the initiation of each cohort after Cohort 1, all safety and available PK data through at least 5 days in the current dose cohort will undergo an unblinded review by the SRC. Following each SRC review, the dose for the next cohort will be endorsed by the SRC and the cohort enrolled according to schedule outlined in the SOE ([Table 3-1](#)).

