### 3.1 SCHEDULE OF ASSESSMENTS

**Table 3-1 Schedule of Events**

Assessment	Screening	Treatment Period			Follow-up				
		Day 1	Days 2-4	Day 5	Day 6	Day 7	Day 8	Day 14±1	Day 28 ±3/ EOS (Early Termination)
Visit Type	Site	Site	Site or Mobile	Site or Mobile	Site	Site or Mobile	Site or Mobile	Site or Mobile	Site
Eligibility criteria	X								
Informed consent a	X								
Demographics	X								
Medical history	X								
Concomitant medications	X	X	X	X	X	X	X	X	X
Physical examination b	X	X	X	X	X	X	X	X	X
Vital signs c	X	X	X	X	X				
12-lead ECG (triplicate-consecutive)	X				X				X
Chemistry/hematology/coagulation d	X	X	Day 2, 4		X		X	X	X
Urinalysis w/ microscopy d	X	X			X		X		
SARS-CoV-2 rapid test, RIDT e	X				X				
Pregnancy testing f	X								
NS1 rapid test g	X								
Pharmacokinetic assessments h		X	Day 2 and Day 3 or 4						
DENV serotype testing i	X								
Viral load j	X	X	X	X	X	X	X	X	X (Day 28 only)
NS1 antigen test	X	X	X	X	X	X	X	X	X (Day 28 only)

Plasma Biomarker	X	X	Day 2, 4		X		X	X	X (Day 28 only)
Adverse events k	X	X	X	X	X	X	X	X	X
Randomization	Prior to dosing								
Study drug administration		X	X	X					
Accountability of returned drug, and review of patient diary					X				X (Early Termination only)

Abbreviations: DENV = dengue virus; ECG = electrocardiogram; ELISA = enzyme-linked immunosorbent assay; NS1 = nonstructural protein 1; RIDT = rapid influenza diagnostic test

- a. Informed consent will be performed before any study procedures are conducted. Results from standard of care evaluations that are available prior to informed consent are accepted if performed within 24 hours of screening
- b. A full physical examination, including height and weight, will be performed at screening and Day 28, except height will not be collected at Day 28. Symptom-directed physical examinations will be performed at the remaining visits.
- c. On Day 1, vital signs should be collected pre-administration of study drug. Vital sign measurements should be performed before any scheduled blood collections. On subsequent days (Days 2-6), vital signs can be collected at any time.  

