**Table 3-2 TID dosing beginning before 10 AM, with 3 doses given on Day 1: Timing of samples for PK, viral load, and NS1**

For TID Dosing (with 3 doses given on Day 1)			
Day	Dose #	PK draw	Viral load and NS1
Day 1	1	Predose	Predose
	2		
	3		
Day 2	4	24 hrs post Dose #1	24 hrs post Dose #1 (prior to Dose #4)
	5		
	6		
Day 3	7	Predose #7 AND 0.5, 1, 2, 4, and 6 hrs post dose #7  NOTE: Serial PK can be done at Dose 7, 8, or 9 (based on site/patient convenience).	48 hrs post Dose #1 (prior to Dose #7)
	8		
	9		
Day 4	10		One sample anytime Day 4
	11		
	12		
Day 5	13		One sample anytime Day 5
	14		
	15		
Day 6			8-24 hrs post Dose #15
Day 7			Any time
Day 8			Any time
Day 14			Any time
Day 28			Any time

**Table 3-3 TID dosing beginning between 10 AM and 4 PM, with 2 doses given on Day 1: Timing of samples for PK, viral load, and NS1**

For TID Dosing (with 2 doses given on Day 1)			
Day	Dose #	PK draw	Viral load and NS1
Day 1	1	Predose	Predose
	2		
Day 2	3	24 hrs post Dose #1 (prior to Dose #4)	24 hrs post Dose #1 (prior to Dose #4)
	4		
	5		
Day 3	6	Predose #7 AND 0.5, 1, 2, 4, and 6 hrs post dose #7  NOTE: Serial PK can be done at Dose 7, 8, or 9 (based on site/patient convenience).	48 hrs post Dose #1 (prior to Dose #7)
	7		
	8		
Day 4	9		One sample anytime Day 4
	10		
	11		
Day 5	12		One sample anytime Day 5
	13		
	14		
Day 6	15		8-24 hrs post Dose #15
Day 7			Any time
Day 8			Any time
Day 14			Any time
Day 28			Any time

**Table 3-4 TID dosing beginning in the evening, with 1 dose given on Day 1:  
 Timing of samples for PK, viral load, and NS1**

For TID Dosing (with 1 dose given on Day 1)			
Day	Dose #	PK draw	Viral load and NS1
Day 1	1	Predose	Predose
Day 2	2		
	3		
	4	24 hrs post Dose #1 (prior to Dose #4)	24 hrs post Dose #1 (prior to Dose #4)
Day 3	5		
	6		
	7	Predose #7 AND 0.5, 1, 2, 4, and 6 hrs post dose #7	48 hrs post Dose #1 (prior to Dose #7)
Day 4	8	NOTE: Serial PK can be done at Dose 7, 8, or 9 (based on site/patient convenience).	One sample anytime Day 4
	9		
	10		
Day 5	11		One sample anytime Day 5
	12		
	13		
Day 6	14		
	15		
			8-24 hrs post Dose #15
Day 7			Any time
Day 8			Any time
Day 14			Any time
Day 28			Any time

**Table 3-5 BID dosing beginning before 4 PM, with 2 doses given on Day 1:  
 Timing of samples for PK, viral load, and NS1**

For BID Dosing (with 2 doses given on Day 1)			
Day	Dose #	PK draw	Viral load and NS1
Day 1	1	Predose	Predose
	2		

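### The visible escalation rule lets the next cohort open before the last-enrolled patients have a post-dose ECG or end-of-treatment laboratory results

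*Protocol*

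**What the plan says.** The rule for opening the next cohort appears in three places in the protocol.

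- Section 5.1.1 (Safety Review Committee) bases it on "an initial safety review by the SRC of available safety data (through Day 5", plus available PK data from the prior cohort.
- Section 3 (Study Design) says that "all safety and available PK data through at least 5 days in the current dose cohort will undergo an unblinded review by the SRC" before each cohort after the first.
- The synopsis (Study Design) uses the same words: "all safety and available PK data through at least 5 days in the current dose cohort".

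Section 5.1.1 also describes what the SRC looks at: "Unblinded safety summaries (e.g., AEs, clinical laboratory test results, vital sign measurements, and 12-lead ECG results) will be reviewed by the SRC".

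Table 3-1 (Schedule of Events) and SAP Section 9.5 place the triplicate 12-lead ECG at screening, Day 6 and Day 28. Table 3-1 places chemistry, hematology and coagulation at screening and on Days 1, 2, 4, 6, 8, 14 and 28, and urinalysis at screening and on Days 1, 6 and 8.

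On the timing of the end-of-treatment visit, Section 3 says: "The Day 6 end of treatment visit will occur 8 to 24 hours after the last dose of study medication is administered". For patients whose first dose is given at mid-day or in the evening of the screening day, it notes that "the last dose of study drug will be administered on Day 6".

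The lines of Section 5.1.1 after the escalation sentence are redacted.

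**The concern.** The SRC is given ECG results to review, but its minimum data cut falls one day before the first post-dose ECG is scheduled. The end-of-treatment blood tests and the only on-study urinalysis before Day 8 also fall on Day 6. A cut at Day 5 therefore excludes the first scheduled look at a patient who has taken the full course.

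This review is the safety gate for escalation. Cohort 1 takes 2250 mg/day, and Cohorts 2 and 3 may take up to 3000 mg/day. According to Protocol Sections 1.2.1 and 1.4, Phase 1 gave single doses up to 1500 mg, but its repeat dosing as described did not exceed 750 mg TID. Repeat dosing at 3000 mg/day thus has no precedent in the protocol. The Day 6 ECG and laboratory tests are the first scheduled evidence after a full course at each new dose in dengue patients.

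**Working it through.** The plan states no figure for this point, so there is none to reproduce. The check sets the SRC cut against the assessment schedule and counts doses from Protocol Tables 3-2 to 3-6.

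**1. Scheduled safety data inside a Day 5 cut, per patient (Table 3-1)**

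- Post-dose ECGs: 0 (next on Day 6).
- Post-dose blood tests: Days 2 and 4 (next on Day 6).
- Urinalysis after Day 1: 0 (next on Day 6).
- Adverse events and vital signs: daily, so inside the cut.

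**2. Doses taken by the end of Day 4 and Day 5**

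Doses by the end of Day d = doses on Day 1 + (d − 1) × doses per day, capped at the course total of 15 (TID) or 10 (BID).

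| Start | Table | Day 1 doses | By end of Day 4 | By end of Day 5 | Left after Day 5 |
|---|---|---|---|---|---|
| TID before 10 AM | 3-2 | 3 | 3 + 9 = 12 | 3 + 12 = 15 | 0 of 15 |
| TID 10 AM to 4 PM | 3-3 | 2 | 2 + 9 = 11 | 2 + 12 = 14 | 1 of 15 (7%) |
| TID evening | 3-4 | 1 | 1 + 9 = 10 | 1 + 12 = 13 | 2 of 15 (13%) |
| BID before 4 PM | 3-5 | 2 | 2 + 6 = 8 | 2 + 8 = 10 | 0 of 10 |
| BID 6 PM to 10 PM | 3-6 | 1 | 1 + 6 = 7 | 1 + 8 = 9 | 1 of 10 (10%) |

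The last blood test before the cut is on Day 4, so it follows at most 10-12 TID doses or 7-8 BID doses. The part of the course with no later blood test inside the cut is at least:

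- TID: 3/15 = 20% to 5/15 = 33%.
- BID: 2/10 = 20% to 3/10 = 30%.

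**3. When the end-of-treatment visit can take place**

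The window is the last dose + 8 h to + 24 h. On the 6 AM / 2 PM / 10 PM example in Section 3.1.2:

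- Last dose 10 PM Day 5: 6 AM to 10 PM on Day 6.
- Last dose 6 AM Day 6: 2 PM on Day 6 to 6 AM on Day 7.
- Last dose 2 PM Day 6 (evening starter): 10 PM on Day 6 to 2 PM on Day 7.

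**4. Reading five days as elapsed time**

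If the cut is 5 × 24 = 120 h after the first dose, with nominal dosing intervals:

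- TID: last dose at 14 × 8 = 112 h, visit at 120-136 h.
- BID: last dose at 9 × 12 = 108 h, visit at 116-132 h.

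Most of the window still lies after the cut, so this reading does not close the gap.

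**5. Size of the dose step**

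- Cohort 1: 750 × 3 = 2250 mg/day.
- Ceiling for Cohorts 2 and 3: 1000 × 3 = 1500 × 2 = 3000 mg/day.
- Ratio: 3000 / 2250 = 1.33, up to 33% more.
- If Cohort 2 is 1000 mg BID: 1000 × 2 = 2000 mg/day, below Cohort 1. The move to 1500 mg BID would then be 3000 / 2000 = 1.5, or 50% more than Cohort 2.

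**The case against.** The strongest objection is the redaction. A block of text in Section 5.1.1 directly after the escalation sentence is blacked out, and further SRC rules could sit there. This stands as a limit: the finding covers the visible text only. It does not remove the finding, because the visible rule itself names a Day 5 cut.

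Second, the synopsis and Section 3 set a floor, Section 5.1.1 calls the review initial, and ECG results are named as review material. Read together, these suggest that the SRC may be expected to wait for Day 6. They permit waiting but do not require it, and the literal reference to Day 5 in Section 5.1.1 points the other way.

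Third, the effect is limited. Earlier-enrolled patients will usually have their Day 6 data by the time of the review. The guaranteed minimum is one patient in 20, who has a 25% chance of being on placebo. Unscheduled tests remain possible. This stands, and the percentages above describe the latest enrollees, not the cohort as a whole.

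Fourth, no known signal makes these data decisive. Section 1.2.1 reports no SAEs, no AEs of Grade 3 or above, no clinically significant ECG changes and no apparent dose relationship for laboratory toxicity. The later doses are ceilings, and Cohort 2 could have a lower daily dose than Cohort 1. All this is correct, but the Phase 1 evidence comes from healthy adults, with no repeat dosing described above 2250 mg/day.

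Fifth, waiting for results from about 40 sites using local laboratories may take longer than the visit itself. Turnaround already applies to the Day 4 results, so what the change adds is mainly the later collection date.

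**Conclusion.** The concern holds. On the visible text, the SRC can open the next cohort without a post-dose ECG or end-of-treatment laboratory results from the last-enrolled patients, some of whom may still have 1 or 2 TID doses or 1 BID dose to take. At a minimum cut this affects at least one patient per cohort; beyond that, the number depends on an enrolment pace that the documents do not give. No analysis or sample size is affected.

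The conclusion assumes that the redacted lines do not already require Day 6 data, and that Day 5 means what Table 3-1 means by it. Confidence is medium because of the redaction. The change should be made: the gap is narrow, but it sits at the escalation gate and is cheap to close.

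**What to change.** Put the same minimum in the synopsis, Section 3 and Section 5.1.1: SRC review takes place after the Day 6 end-of-treatment visit is complete, with ECG and laboratory results available, for all patients in the cohort who are still in the study. State also whether escalation waits for any replacement block enrolled under Section 4.3.3. If the redacted text already contains such a requirement, aligning the three visible statements with it is enough.

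No visit, test or sample is added. The ECG gained is a post-treatment one, taken 8 to 24 hours after the last dose; the change does not provide an ECG during dosing.

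The cost is wording in three places and a wait of about one day per cohort, running into Day 7 for evening TID starters. With two escalation decisions, that is 2 × 1 = 2 to 2 × 2 = 4 days over the study, assuming Day 6 results are returned about as quickly as Day 4 results.

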### 5.2 INVESTIGATIONAL PRODUCTS

The study drugs that will be used are as follows:

Product	Supplied Formulation
AT-752 tablet	250 mg of AT-281, free base of the drug substance AT-752
Matching placebo tablet	0 mg of AT-281, free base of the drug substance AT-752

Further information on the study drug can be found in the investigator’s brochure ([Atea Pharmaceuticals](#)).

### 5.2.1 Study Drug Packaging and Storage

Atea Pharmaceuticals, Inc. will provide the investigator and clinical unit with adequate quantities of AT-752 and matching placebo. Detailed instructions for the preparation of study treatments will be provided separately to the pharmacy.

All study drugs must be stored according to the labeled instructions in a secure cabinet or room with access restricted to necessary clinic personnel. The site will be required to keep a temperature log to establish a record of compliance with storage conditions.

The storage condition for AT-752 and placebo is: 15 - 25°C.

### 5.2.2 Study Drug Accountability

The investigator will maintain accurate records of receipt of all study drugs, including dates of receipt. Accurate records will be kept regarding when and how much study drug is dispensed and used by each subject in the study. Reasons for departure from the expected dispensing regimen must also be recorded. At the completion of the study, and to satisfy regulatory requirements regarding drug accountability, all study drugs will be reconciled and retained or destroyed according to applicable regulations.

## 5.3 METHOD OF ASSIGNING SUBJECTS TO TREATMENT GROUPS

CCI will generate the randomization schedule. Eligible subjects will be enrolled into the current dose cohort at a ratio of 3:1 (active:placebo). Each subject will be randomly assigned to a treatment assignment through a centralized randomization process and will receive a unique randomization number linked to the blinded treatment assignment. Randomization will be stratified by geographic region.

CCI [REDACTED]  
[REDACTED]  
[REDACTED]  
[REDACTED]  
[REDACTED]  
[REDACTED]  
[REDACTED]  
[REDACTED]

CCI [REDACTED]  
[REDACTED]  
[REDACTED]  
[REDACTED]  
[REDACTED]  
[REDACTED]  
[REDACTED]  
[REDACTED]  
[REDACTED]  
[REDACTED]  
[REDACTED]  
[REDACTED]

